3.3 Secondary Aims

The secondary aims of this study are to evaluate

- Route of delivery
- Indications for cesarean section (uncontrolled hypertension, failure to progress, non-reassuring fetal well-being, etc)
- Maternal hypotension (<30% baseline or mean arterial pressure $<$ 65 mmHg)

- Time from enrollment to hospital discharge
- Postpartum hypertension control, including frequency and dosing of acute or maintenance antihypertensive therapy
- Composite of adverse maternal outcomes (time duration to need for acute antihypertensive therapy, receipt of second dose study drug, time from randomization to delivery, seizure, adverse CNS outcome (stroke or cortical blindness), pulmonary edema, oliguria, DIC, admission to ICU, dialysis, mechanical ventilation, abruption, post-partum hemorrhage, receipt of blood products, maternal death)
- Composite of adverse neonatal outcomes (intrapartum fetal demise, abruption, neonatal death, Apgar score <7 at 5 minutes, intubation, convulsions, IVH, confirmed sepsis, RDS requiring O2, NICU admission)

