3.5 Population and Eligibility Criteria

a) Setting: This single center study will be conducted at The Ohio State University Wexner Medical Center.

b) Inclusion criteria:

1. Women aged 18-45 with a viable single or twin intrauterine pregnancy between 22 0/7 and 41 6/7 weeks gestation based on the best obstetric estimate by ACOG criteria.
2. Diagnosis of preeclampsia with severe features with decision made to induce labor. The patient may or may not have already received acute treatment for severe blood pressures.

c) Exclusion criteria:

- Known allergy or adverse reaction to Nifedipine or any medical condition where Nifedipine is contraindicated, such as galactose intolerance, severe GI stricture, and GI hypomotility disorder.
- Currently receiving Nifedipine XL as part of hypertension management prior to induction of labor
- Participation in another trial that affects the primary outcome without prior approval
- Physician/provider or patient refusal

- Participation in this trial in a prior pregnancy
- Triplet or higher order pregnancy

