3.6 Gestational Age Determination

Gestational age is determined using criteria proposed by the American Congress of Obstetricians and Gynecologists, the American Institute of Ultrasound in Medicine, and the Society for Maternal-Fetal Medicine, and is denoted “project gestational age.” The “project EDC,” which is based on the project gestational age, cannot be revised once a determination has been made. If the pregnancy is conceived by in-vitro fertilization, project gestational age is calculated from the date of embryo transfer and the embryo age at transfer. If the pregnancy is conceived spontaneously (including ovulation induction and artificial insemination) information from the earliest dating ultrasound and the last menstrual period are used to determine project gestational age. If no dating ultrasound has been performed previously, one must be performed before the patient can be randomized.

The following algorithm is used:

- The first day of the last menstrual period (LMP) is determined, and a judgment made as to whether or not the patient has a “sure” LMP date.
- If the LMP date is unsure, ultrasound measurement(s) obtained at the patient’s first dating ultrasound examination is used to determine the project gestational age. If the first dating ultrasound was conducted before 14 weeks 0 days, the measurement must be based on crown rump length (CRL).
- If the LMP date is sure, project gestational age is determined by a comparison between the ultrasound measurements based on the earliest dating ultrasound. If the ultrasound confirms the gestational age by LMP as in the table below, the LMP-derived gestational age is used to determine the project gestational age. Otherwise, project gestational age will be determined based upon the ultrasound measurement.

Table 1. Cutoffs for using LMP to determine gestational age for sure LMP

Gestational age at first ultrasound by LMP	Ultrasound agreement with LMP
up to 8 6/7 weeks (by CRL)	≤5 days
9 0/7 weeks to 13 6/7 weeks (by CRL)	≤7 days
14 0/7 to 15 6/7 weeks	≤7 days
16 0/7 to 21 6/7 weeks	≤10 days

*CRL = Crown Rump Length

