3.7 Randomization Method and Masking

Randomization may occur upon confirmation that all inclusion/exclusion criteria are satisfied, after verification of participant consent and HIPAA authorization.

Consenting women will be randomly assigned to nifedipine 30XL and placebo in a 1:1

ratio according to a randomization sequence prepared by and maintained by independent statistician and available from central investigational pharmacy who will dispense study drug or placebo. The two study arms are double masked; neither the patient nor the clinical staff will be aware of the treatment assignment.

The simple blocked randomization method will be used to generate the randomization sequences because it provides a high probability of balance in treatment assignments, it is unpredictable, and it allows an explicit randomization analysis to be conducted with relative ease.

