4.2 Randomization and Baseline Visit Procedures

Randomization may occur upon confirmation that all inclusion/exclusion criteria are satisfied, after verification of participant consent and HIPAA authorization. Study staff will also verify participant contact information and obtain a Release of Information, as permitted by local policy, to collect outcome and serious adverse event (SAE) documentation. Patients will be assigned next sequential number and central pharmacy will dispense study drug or placebo depending on randomization allocation sequence.

Once the patient is randomized, the patient will receive a study drug or placebo from clinical nurse. She will be instructed to take 1 pill daily until delivery.

In addition to information collected for eligibility, gestational age, and EDC determination, the following information will be obtained at randomization from a patient interview followed by a review of her chart:

- Demographic information: age, race, insurance status
- Medical history: pre-pregnancy weight, current weight, height, chronic disease history
- Obstetrical history including outcomes of all prior pregnancies and which pregnancy(ies) was complicated by preeclampsia.
- Social history: marital status, years of education, alcohol use, tobacco use, and maternal drug use
- Record baseline blood pressure, and baseline preeclampsia laboratory data including platelets, creatinine, liver function tests and proteinuria status, if performed
- Medication use e.g. ASA prior to enrollment, antihypertensive medications including prior administration of acute antihypertensive medications, metformin, anti-platelet agents, etc

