2.6 Statistical Analysis Plan

Standard comparisons of characteristics between groups will be conducted at baseline. It

is anticipated that the randomization scheme will balance the groups for these covariates and they will not be adjusted for in the primary analysis.

The primary analysis will compare incidence of the outcome between the 2 study groups. If the two groups show a difference in the incidence of the primary outcome, interactions will be evaluated and subgroup analyses conducted to determine whether the effect prevails.

Lost to follow up should not occur given study design and no follow up is scheduled. Since many of the secondary endpoints are dichotomous variables like the primary outcome, standard statistical methods for rates and proportions will be appropriate. Continuous variables will be compared using standard statistical methods,

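### Section 2.6 plans no gestational-age-adjusted analysis of the neonatal composite, giving up precision that a value fixed before randomization would supply at almost no cost

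*Combined protocol and SAP*

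**What the plan says.** - **Population (3.5).** "Women aged 18-45 with a viable single or twin intrauterine pregnancy between 22 0/7 and 41 6/7 weeks gestation". The decision to induce has already been made at entry.
- **Randomization (3.7).** Allocation is 1:1. "The simple blocked randomization method will be used to generate the randomization sequences". No stratification factor is named.
- **Neonatal composite (3.3).** Ten components. They include neonatal death, intubation and IVH, and the list ends with "RDS requiring O2, NICU admission". It is one of several secondary aims. No event rate is given anywhere, and the plan does not say whether it is counted per woman or per infant.
- **Gestational age (3.6 and 4.2).** "If no dating ultrasound has been performed previously, one must be performed before the patient can be randomized". Section 4.2 lists the other baseline items as "In addition to information collected for eligibility, gestational age, and EDC determination", so gestational age is on file for each woman.
- **Analysis (2.6).** Baseline characteristics are compared between arms. Balance is expected from randomization, and covariate adjustment is ruled out for the primary analysis. For the dichotomous secondary endpoints, "standard statistical methods for rates and proportions will be appropriate". No covariate, stratum or adjusted analysis is named for the neonatal composite.

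**The concern.** Women are enrolled once induction is decided, so gestational age at randomization is close to gestational age at birth and is almost entirely fixed before treatment. For an outcome containing IVH, RDS, intubation and NICU admission, it should be a strong predictor in both arms. Across nearly 20 weeks of gestation, much of the woman-to-woman variation in the composite may therefore be explainable by something already recorded. An analysis that ignores it leaves that variation in the standard error.

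Two things are at stake. The first is precision: a real difference in either direction is harder to see. The second is interpretation: if one arm happens to draw more early-preterm women, the baseline table will show it, but 2.6 says nothing about what to do next. Any adjusted analysis would then be chosen after seeing the data. Sections 2.0 and 2.1 themselves raise uterine hypoperfusion and non-reassuring fetal status after a fall in maternal pressure, so the neonatal result will be read with interest.

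The point concerns the neonatal composite only.

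**Working it through.** **Inputs from the documents.** N = 110, so n = 55 per arm at 1:1. This total was set for the primary outcome (section 5.0) and is taken as given. The plan has no figure for the neonatal composite to reproduce.

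**Assumed inputs.** The documents give no gestational-age mix or composite risks. Two cases, for <34, 34-36 and ≥37 weeks:

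| Case | Mix | Composite risk |
|---|---|---|
| Strong association | 25/35/40% | 95/50/15% |
| Weak association | 20/30/50% | 70/40/20% |

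**Step 1: share of outcome variance explained.** With stratum weights w and risks p, overall risk P = Σwp and R² = 1 − Σw·p(1−p) / [P(1−P)].

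- Strong: P = 0.2375 + 0.1750 + 0.0600 = 0.4725; P(1−P) = 0.2492; Σw·p(1−p) = 0.0119 + 0.0875 + 0.0510 = 0.1504; R² = 0.397.
- Weak: P = 0.14 + 0.12 + 0.10 = 0.36; P(1−P) = 0.2304; Σw·p(1−p) = 0.042 + 0.072 + 0.080 = 0.194; R² = 0.158.

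**Step 2: standard error of the risk difference.** Unadjusted √[2P(1−P)/55]; stratified approximately √[2Σw·p(1−p)/55]; ratio √(1−R²).

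- Strong: 0.095 to 0.074, ratio 0.777, a 22% cut, worth 1/0.603 = 1.66 times the sample size.
- Weak: 0.092 to 0.084, ratio 0.918, an 8% cut, worth 1/0.842 = 1.19 times.

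**Step 3: power by simulation (55 per arm, two-sided 5%).** Unadjusted z-test against the Cochran-Mantel-Haenszel (CMH) test in three bands. The odds ratio applies within each stratum.

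| Odds ratio | Strong: unadjusted → CMH | Weak: unadjusted → CMH |
|---|---|---|
| 0.4 | 26% → 41% | 44% → 49% |
| 1.5 | 9% → 13% | 14% → 15% |
| 2.0 | 20% → 29% | 32% → 37% |

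**Step 4: type I error.** With no drug effect, rejection was 4.6-6.2% unadjusted and 5.6-5.7% by CMH in 4,000 trials per case. In 20,000 trials for each of four other mixes (below) it was 4.6-5.0% and 4.8-5.0%, with mean bias about zero. Neither method is invalid.

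**Step 5: chance imbalance, strong case.** The SE of the arm difference in the share under 34 weeks is √(2 × 0.25 × 0.75/55) = 0.0826, so P(difference ≥ 10 points) ≈ 0.23. Risk in the other two bands combined is (0.175 + 0.060)/0.75 = 0.313. A 10-point difference therefore moves the composite by (0.95 − 0.313) × 0.10 = 6.4 points with no drug effect, which is 0.67 of the unadjusted SE of 9.5 points. In no-effect trials with an imbalance that large or larger, the unadjusted test was falsely significant in about 11% and CMH in about 5%.

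**Step 6: other mixes.** Assumed, with blocks of 4.

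| Mix; risks | SE unadjusted → stratified | Power at OR 0.4 |
|---|---|---|
| A: 20/35/45%; 95/50/15% | 0.094 → 0.076 | 28% → 42% |
| B: 35/35/30%; 98/50/15% | 0.095 → 0.070 | 20% → 38% |
| C: 10/30/60%; 95/40/12% | 0.085 → 0.072 | 25% → 35% |
| D (extreme): 40/20/40%; 100/40/5% | 0.096 → 0.049 | 8% → 18% |

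The SD of the shift due to imbalance alone is 4.8-6.5 points in A-C and 8.2 in D. As a share of the unadjusted variance that is (0.048/0.085)² = 32% in C, 38% in A, 47% in B and (0.082/0.096)² = 73% in D. Imbalance is the larger part only in the extreme case.

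**The case against.** The case for leaving the plan alone has real force.

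- *No validity error.* Chance imbalance is already counted in the unadjusted standard error. This stands: step 4 shows no bias and about 5% error overall. The 11% in step 5 is conditional on a sizeable imbalance.
- *The plan does not prescribe raw proportions.* CMH is itself a standard method for proportions, and 2.6 excludes adjustment only for the primary analysis. This stands too: the fault is silence, not a wrong choice. But the phrase fixes no covariate and no bands, so an adjusted analysis made under it would not be prespecified.
- *The gain rests on assumptions.* Correct. In the weak case it is 5 points of power. The direction was the same in every mix tried at an odds ratio of 0.4; the size is uncertain.
- *Adjustment does not make this a safety test.* Correct. At an odds ratio of 1.5, power stays at about 13-15% when stratified. Sections 1.4 and 3.3 list the composite among secondary aims and give it no gatekeeping role.
- *One result per woman is a separate decision.* True. Twins are eligible and the plan sets no unit, but the test needs independent units, so the choice has to be written down.

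A reader might infer that gestational-age imbalance overwhelms the neonatal comparison, or that its result would mainly show which arm drew more early-preterm women. The documents do not support that. They give no mix or risks from which it could follow. In both main cases gestational age explains a minority of the outcome variance (40% and 16%), and only the extreme mix D makes imbalance dominant.

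**Conclusion.** The gap is real and modest. Eligibility is wide, no stratification factor is named, gestational age is known for every woman before randomization, and no adjusted analysis of the neonatal composite is prespecified. The unadjusted comparison remains valid. What is lost is precision: an 8-22% larger-than-necessary standard error, measured as the cut from stratifying, and 5 to 15 points of power at an odds ratio of 0.4 in the two main cases. There is also no agreed answer if this one trial is imbalanced. All these sizes depend on assumed mixes and risks and should be rechecked against the site's own data. The smallest difference detectable with 80% power in the strong case is about 2.8 × 0.095 = 27 points unadjusted and 2.8 × 0.074 = 21 points stratified, so a null result would not rule out moderate harm either way. This is an inexpensive efficiency improvement to an unpowered secondary endpoint, not the correction of an invalid analysis.

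**What to change.** Add to 2.6, in words such as: *The neonatal composite, scored once per woman (any affected infant), will be compared between arms with a Mantel-Haenszel risk difference and a Cochran-Mantel-Haenszel test stratified by project gestational age at randomization (<34 0/7, 34 0/7-36 6/7, ≥37 0/7 weeks). Unadjusted proportions will be shown alongside.*

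The cost is one sentence and no new data. The bands and the per-woman rule must be fixed before unblinding. Randomization, trial conduct and the primary analysis stay as they are; stratified randomization is optional. The report should also give the confidence interval and say that the trial cannot exclude moderate neonatal harm.

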6.0 Data Management

6.1 Data Collection Forms

Data will be collected on standardized forms on which nearly all responses have been pre-coded. Each form is briefly described below.

- Screening Log
- Eligibility Checklist
- Randomization: completed for all eligible women, lists randomized drug code number
- Baseline Form: includes detailed demographic and social data, medical & obstetrical history, and current pregnancy complications (to date), as applicable
- Study Drug lots: documents dispensing of study medication and the return of any unused study medication
- Maternal delivery and outcome forms: documents labor, delivery and postpartum information through the first 7 days after delivery
- Neonatal baseline form: records date and time of birth, delivery data and status at delivery for each fetus/infant
- Neonatal outcome form: records outcome data for all infants admitted to the NICU or special care nursery
- Patient status form: documents loss to follow-up/withdrawal status, side effects since the last dose
- Will do an intrapartum BP log.

